- Update the product complaint reporting contact information.
- Correct typographical errors, punctuation, grammar, and formatting.

For specific examples of changes in text and where the changes are located, see Section [15.12](#).

PROTOCOL SUMMARY

Study Title: An Open-Label, Dose-Escalation, Phase 1 Study of the Oral Formulation of MLN9708 Administered Weekly in Adult Patients With Relapsed or Refractory Light-Chain (AL) Amyloidosis Who Require Further Treatment

Study Phase: 1

Number of Patients: Overall, as many as 50 patients will be enrolled in the study.

Study Objectives

Primary Objectives

[figure not shown]
- To determine the safety, tolerability, and maximum tolerated dose (MTD) of oral MLN9708 administered weekly in patients with previously treated relapsed or refractory light-chain (AL) amyloidosis
- To determine the recommended phase 2 dose (RP2D) of oral MLN9708 administered weekly

Secondary Objectives

- To characterize the plasma PK and whole blood pharmacodynamic effect of MLN9708 in this patient population
- To assess the rate of organ response and organ improvement according to standardized criteria
- To assess overall hematologic response rate (complete response [CR], very good partial response [VGPR], and partial response [PR])
- To assess time to hematologic and organ response, respectively
- To assess duration of hematologic and organ response, respectively
- To determine time to hematologic and organ disease progression, respectively
- To assess progression free survival (PFS)
- To assess overall survival including 1-year survival rate

Exploratory Objectives

CCI

Overview of Study Design:

The study will include patients with previously treated systemic AL amyloidosis who require further therapy and will be aimed at determining the safety profile and the MTD/RP2D of MLN9708 administered orally. A 3 + 3 dose-escalation scheme will be implemented. Patients will receive escalating doses of MLN9708 PO on Days 1, 8, and 15 in a 28-day cycle in the absence of disease progression or unacceptable toxicity. If there is no hematologic response (CR + VGPR + PR) after completion of 3 cycles of single-agent MLN9708, dexamethasone will be added on Days 1 to 4 of every cycle (Days 1-4 every 28 days) beginning with Cycle 4. The patient's response status will be reassessed after 3 additional cycles; if there is no hematologic response at that time, the patient will be removed from treatment and followed for survival.

The estimated safe starting dose of MLN9708 will be selected from the dose-escalation portion of

the C16004 study, a phase 1 study of weekly dosing in patients with relapsed and refractory multiple myeloma. The starting dose will be at least 1 dose level below the C16004 MTD (if it has been reached by the time this study starts) and, if not, then a dose level completed without documented dose-limiting toxicity (DLT).

DLTs will be assessed in Cycle 1 only. In the context of emerging clinical data of single-agent MLN9708, dose-escalation of MLN9708 will continue until the MTD has been identified or a maximum planned dose (MPD) is determined to be safe.

Once the MTD/RP2D has been established, 2 expansion cohorts of patients with relapsed or refractory amyloidosis, including approximately 10 proteasome inhibitor-naïve patients and approximately 16 proteasome inhibitor-exposed patients, will be treated at the MTD/RP2D to more fully characterize the safety, tolerability, and efficacy of MLN9708, and the PK and pharmacodynamics of MLN9708 in this patient population. As many as 30 patients will be enrolled in the dose-escalation portion of the study, and as many as 20 additional patients (26 in total, including 6 patients from the dose-escalation portion) will be enrolled in the expansion cohorts.

Toxicity will be evaluated according to the investigators' documentation of adverse events (AEs) using the National Cancer Institute Common Terminology Criteria for Adverse Events, version 4.03. AEs will be assessed, and laboratory values, vital signs, and ECGs will be obtained to evaluate the safety and tolerability of MLN9708.

Patients will be evaluated at scheduled visits over 4 study periods: Screening, Treatment, End of Treatment (EOT), and Follow-up (progression-free and overall survival). Patients will discontinue treatment if they experience PD or unacceptable toxicity. The maximum duration of treatment with either single-agent MLN9708 or MLN9708 plus dexamethasone, however, will be 12 cycles unless after discussion between the investigator and the sponsor, it is determined that a patient would derive benefit from continued therapy beyond 12 cycles.

The primary determinant of response for the purpose of continuing treatment is the hematologic response. Response will be determined according to standardized criteria. Hematologic response assessments are conducted after every cycle during treatment, at the end of treatment visit, and then every 6 weeks thereafter until disease progression or initiation of subsequent antineoplastic therapy. A bone marrow aspirate and biopsy are to be obtained at the Screening visit and may be repeated at the discretion of the investigator as clinically indicated and if CR is documented by other parameters in the standardized criteria.

Amyloid-related organ assessments are to be performed for all patients at screening; after Cycles 3, 6, 9, and 12; every 6 months thereafter until disease progression or the initiation of subsequent antineoplastic therapy; and at the End-of-Treatment visit. An evaluation of disease response according to standardized criteria will be performed at regular predefined intervals during treatment and then at regular intervals during follow up. Radiological evaluations (skeletal surveys, chest X-rays, computed tomography [CT] scan, or magnetic resonance imaging [MRI]), echocardiograms, blood samples and 24-hour urine collections (M-protein quantification, serum free light chain assay, immunofixation of serum and urine, quantification of immunoglobulins, serum cardiac markers) and bone marrow biopsy and aspirates will be employed to assess the status of the patient's disease response.

Quality of life (QOL) will be assessed only for patients in the expansion cohorts using the European Organization for Research and Treatment of Cancer QLQ-C30 (EORTC-QLQ-C30).

A blood sample will be collected for preparation of genomic deoxyribonucleic acid that will be used, as needed, to assess potential relationships **CC1** [REDACTED], clinical response, and safety.

Electrocardiograms will be acquired on Day 1 of Cycles 1 through 12 and at EOT and a 24-hour Holter monitor will be used at screening.

[figure not shown]
Study Population:

Adult patients 18 years or older with biopsy-proven systemic AL amyloidosis with relapsed or refractory disease after at least 1 prior therapy that, in the investigator's opinion, requires further treatment. If a patient has received a transplant as his/her first therapy, he/she must be at least 3 months posttransplantation and recovered from the side effects of the stem cell transplant. Patients who were not candidates for high-dose therapy and were unable to tolerate an alkylating agent plus a corticosteroid (eg, melphalan plus prednisone) or patients who are intolerant to an alternative prior therapy after receiving at least 1 cycle of such therapy because of severe adverse events (eg, hypersensitivity reaction) can be considered for enrollment after discussion with the Millennium clinician.

Duration of Study: The duration of enrollment will be approximately 24 months.

It is anticipated that this study will last for approximately 84 months. The duration of follow-up for OS will be 60 months after the last patient enters treatment. Treatment may be continued in this study or in a MLN9708 rollover study, if and when such a study is made available, upon request by the investigator and agreement by the project clinician.

Study Overview Diagram

Schedule of Events

Study Procedures	Screening ^a	Treatment Period					End of Treatment ^d	Follow-up			
		CYCLES 1 -12 ^b									
	Days	Days									
	-28 to -1	1 ^c	8	15	Rest Period 22 to 28	PFS ^e (± 1 wk)		OS ^f (± 1 wk)			
Informed Consent	X										
Inclusion/Exclusion criteria	X										
Demographics	X										
Complete Medical History, including AL amyloidosis treatment history, neurologic history, and cardiac medical history	X										
12-lead ECG (RR, PR, QRS, QT, QTc, and waveforms)	X	X					X				
24-hour Holter monitor ^g	X										
Physical Examination	X	X ^h					X	Per MD practice			
ECOG Performance Status	X	X ⁱ					X				
Vital Signs	X	X					X	Per MD practice			
Height	X										
Weight (kg)	X	X					X				
Pregnancy Test ^j	X	X									
Hematology ^k	X	X	X	X	X	X					
Clinical Chemistry ^k	X	X	X	X	X	X					
Urinalysis	X						X				
24-hour urine collection for creatinine and total protein	X				X ^l	X	X ^l				
Coagulation studies (PT/INR; PTT) ^m	X										

Study Procedures	Screening ^a	Treatment Period				End of Treatment ^d	Follow-up		
		CYCLES 1 -12 ^b					PFS ^e (± 1 wk)	OS ^f (± 1 wk)	
	Days	Days					Every 6 weeks	Every 12 weeks	
	-28 to -1	1 ^c	8	15	Rest Period 22 to 28				
Thyroid stimulating hormone (TSH); random cortisol level	X								
Blood Sample for Genotyping	X								
Neurologic examination	X	X				X	X ^e		
QOL Assessment ^h	X				X	X			
PK and Whole blood 20S proteasome activity		See table below for detailed sampling schedule							
Response Assessment									
Hematological Disease Response Assessment ^o					X	X	X		
β2-microglobulin	X								
M-protein measurements (SPEP)	X				X	X	X		
M-protein measurements (UPEP [24-hour urine collection])	X				X	X	X		
Serum free light chain assay	X				X	X	X		
Immunofixation - serum and urine	X				X	X	X		
Quantification of Ig	X				X	X	X		
Bone marrow biopsy/aspiration	X ^p				X ^q	X	X ^q		
Skeletal Survey ^r	X				X	X	X		
Amyloid-related organ assessment ^{s,t}	X								
Posteroanterior and lateral CXR	X								
CT or MRI scans as indicated to assess organ involvement (eg, lung; liver) ^{s,u}	X								
Echocardiogram ^s	X				X	X	X		
Estimates of interventricular septal and posterior wall thickness ^s	X				X	X	X		

Study Procedures	Screening ^a	Treatment Period				End of Treatment ^d	Follow-up		
		CYCLES 1 -12 ^b					PFS ^e (± 1 wk)	OS ^f (± 1 wk)	
	Days	Days					Every 6 weeks	Every 12 weeks	
	-28 to -1	1 ^c	8	15	Rest Period 22 to 28		Every 6 weeks	Every 12 weeks	
Serum cardiac markers (NT-proBNP, BNP, troponin T or I) ^s	X				X	X	X		
NYHA classification	X	X				X	X		
Adverse Events		Recorded from the first dose of study drug through 30 days after last dose of study drug or until the initiation of subsequent antineoplastic therapy							
Serious Adverse Events		Recorded from the time informed consent is signed through 30 days after the last dose of study drug							
Concomitant Medications/Procedures		Recorded from the first dose of study drug through 30 days after last dose of study drug or until the initiation of subsequent antineoplastic therapy							
Study Drug Administration									
MLN9708		X	X	X					
Dexamethasone (only if no response after 3 cycles of single-agent MLN9708)		X							
Survival								X	

Abbreviations: BNP = B-type natriuretic peptide; CT = computed tomography CXR = chest X-ray; ECG = electrocardiogram; ECOG = Eastern Cooperative Oncology Group; EMG = electromyography; EOT = end of treatment; Ig = immunoglobulin; INR = international normalized ratio; MRI = magnetic resonance imaging; NT-proBNP = N-terminal proBNP; OS = overall survival; PD = progressive disease; PFS = progression-free survival; PK = pharmacokinetics; PT = prothrombin time; PTT = partial thromboplastin time; QOL = quality of life; SPEP = serum protein electrophoresis; UPEP = urine protein electrophoresis.

a Evaluations including CT scans, MRIs, and skeletal surveys may be performed within 8 weeks of the first dose of study drug.

b One complete cycle is 28 days. In order to begin a new cycle of treatment, certain criteria must be met (see Section 6.5.2). Patients who do not continue study treatment dosing after Cycle 1 must complete the EOT and follow-up assessments.

c All evaluations/procedures are to be conducted on Day 1 of the stated cycle before dosing or within 3 days before the first dose of drug unless otherwise specified.

d Patients who do not continue treatment must complete the EOT assessments, which should occur at least 30 days after the last dose of study drug or prior to

Study Procedures	Screening ^a	Treatment Period					End of Treatment ^d	Follow-up	
		CYCLES 1 -12 ^b						PFS ^e (± 1 wk)	OS ^f (± 1 wk)
	Days	Days				Every 6 weeks		Every 6 weeks	Every 12 weeks
	-28 to -1	1 ^c	8	15	Rest Period 22 to 28	Every 6 weeks		Every 12 weeks	Every 12 weeks

the initiation of subsequent antineoplastic therapy.

- e Conducted from EOT until occurrence of PD or the initiation of subsequent antineoplastic therapy. If a patient comes off treatment due to PD, they should continue to be followed for OS long-term follow-up. Hematologic response assessments should be conducted every 6 weeks (± 1 week) during PFS follow-up while amyloid organ response assessments should be conducted every 6 months, including a neurologic examination in patients with persistent neurologic symptoms and clinical examinations in patients with persistent symptoms thought by the investigator to be amyloid-disease related (see Section 7.5.12).
- f Conducted every 12 weeks (± 1 week) after PD or the initiation of subsequent antineoplastic therapy. Data may be collected by methods that include but are not limited to telephone, e-mail, mail, and social security indexes.
- g 24-hour Holter monitor, to be performed at screening, and at any time the physician believes it is medically appropriate.
- h A full physical exam will occur every 3 cycles. Symptom-directed assessments will be conducted per standard clinical practice.
- i Should occur every 3 cycles.
- j A serum pregnancy test will be performed for women of childbearing potential during screening and predose on Cycle 1, Day 1. The serum pregnancy test may be collected up to 3 days before dosing. The results must be available and negative before the first dose of MLN9708 is administered.
- k Hematology and chemistry panels may be collected up to 3 days prior to dosing. Criteria for retreatment are provided in Section 6.5.2. After 24 cycles on treatment, hematology and chemistry laboratory evaluations may be done to monitor the patient according to standard clinical practice per the treating physician.
- l Repeat as clinically indicated by change in serum creatinine. Creatinine clearance will be calculated based on a 24-hour urine collection at screening. eGFR will be calculated according to the equations in Section 15.1. 24-hour urine for protein is required to assess amyloid renal involvement/ response.
- m If abnormal, a diagnostic work up should be performed and the patient treated and stabilized before administering MLN9708. PT/INR and PTT may be repeated during the treatment period at the discretion of the investigator if bleeding occurs or as clinically indicated.
- n Only for patients in the extension cohort after every cycle.
- o Repeat every treatment cycle, at the EOT visit, and every 6 weeks during the PFS follow-up period.
- p CCI
- q Bone marrow biopsy and aspirate should be repeated at the discretion of the investigator as clinically indicated and if response is documented by other parameters, and at EOT. Immunohistochemistry of dominant clonal plasma cells is recommended.
- r To be performed at screening and at any time the physician believes there are symptoms or signs that suggest increased or new bone lesions. Plain films of symptomatic sites for signs or symptoms of new bone lesions may be obtained instead of a full skeletal survey. A PET-CT may be done at screening in

Study Procedures	Screening ^a	Treatment Period					End of Treatment ^d	Follow-up	
		CYCLES 1 -12 ^b						PFS ^e (± 1 wk)	OS ^f (± 1 wk)
	Days	Days				Every 6 weeks		Every 6 weeks	Every 12 weeks
	-28 to -1	1 ^c	8	15	Rest Period 22 to 28	Every 6 weeks		Every 12 weeks	Every 12 weeks

place of a skeletal survey provided that the same modality for assessment is used throughout the study. If results are interpreted as abnormal, then repeat at the discretion of the investigator as clinically indicated. The same imaging modality used at screening should be used for all follow-up assessments.

s At baseline, Cycles 3, 6, 9, and 12, and every 6 months thereafter until disease progression or the initiation of subsequent antineoplastic therapy.

t The following tests should be included for organ assessments:

heart: NT-proBNP, BNP, troponin, echocardiography, physical examination;

kidney: 24-hour urine proteinuria, serum creatinine, eGFR, serum albumin;

liver: alkaline phosphatase, ALT, ultrasound/CT scan/ MRI (as indicated);

peripheral nervous system: patient reported symptoms, physical examination, electromyography (EMG; if indicated);

autonomic nervous system: patient reported symptoms, determination of postural hypotension;

gastrointestinal: patient reported symptoms;

soft tissue: physical examination, imaging as indicated

u If results are interpreted as abnormal, then repeat at the discretion of the investigator as clinically indicated except if being used to monitor amyloid liver involvement. The same imaging modality used at screening (CT/MRI) should be used for all follow-up assessments.

Pharmacokinetic & Pharmacodynamic Sampling (Cycle 1)

	Day 1 ^a						Day 2	Day 8		
	Minutes		Hours							
	Predose (within 1 hour of dosing)	MLN9708	30 (± 5)	1 (± 0.25)	2 (± 0.25)	4 (± 0.75)	6 (± 0.75)	24 (± 1.0)	168 (± 4.0) [prior to Day 8 dose]	
PK (whole blood & plasma)	X		X	X	X	X	X	X	X	
Whole blood 20S proteasome activity	X		X	X	X	X	X	X	X	
		Day 15						Day 16	Day 22	
		MLN9708	Minutes		Hours					
	Predose (within 1 hour of dosing)		30 (± 5)	1 (± 0.25)	2 (± 0.25)	4 (± 0.75)	6 (± 0.75)	24 (± 1.0)	168 (± 4.0)	
PK (whole blood & plasma)	X		X	X	X	X	X	X	X	X
Whole blood 20S proteasome activity	X		X	X	X	X	X	X	X	X

The following samples will be collected at each time point: 1 blood sample (3 mL) for the determination of plasma concentrations of MLN2238, 1 blood sample (3 mL) for the determination of whole blood concentrations of MLN2238, and 1 blood sample (1 mL) for the measurement of whole blood 20S proteasome activity.

a Day 1, 2 and 8 samples are ONLY collected at the MTD; however, Day 15, 16 and 22 are collected for all patients.

TABLE OF CONTENTS

LIST OF TABLES	16
LIST OF FIGURES.....	16
LIST OF ABBREVIATIONS AND GLOSSARY OF TERMS	17

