3.2 Secondary Endpoints

[figure not shown]
The secondary endpoints include:

- Single- (MTD cohort) and multiple-dose plasma PK after oral MLN9708
- Whole blood 20S proteasome activity profile and inhibition parameters of multiple-dose oral MLN9708
- Organ response and organ improvement according to standardized criteria
- Overall hematologic CR + VGPR + PR
- Time to organ or hematologic response, measured as the time from the first dose of MLN9708 to the date of first documentation of a confirmed organ or hematologic response, respectively
- Duration of organ or hematologic response, measured as the time from the date of first documentation of a confirmed organ or hematologic response to the date of confirmed organ or hematologic disease progression, respectively
- Time to organ and hematologic progression, measured as the time from the date of the first dose of MLN9708 to the date of first documented organ or hematologic disease progression
- Organ and hematologic disease PFS, defined as the time from the date of the first dose of MLN9708 to the date of confirmed organ or hematologic disease progression or death, respectively.

- One-year survival, defined as the patient survival probability at 1 year after the date of first dose of MLN9708

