A 3 + 3 dose-escalation scheme will be implemented and dose intervals will follow those outlined in Section 6.4. Although DLTs may occur at any point during treatment, only DLTs occurring during Cycle 1 of treatment in the phase 1 portion will necessarily influence decisions regarding dose-escalation, expansion of a dose level, or evaluation of intermediate dose levels. In the context of emerging clinical data of single-agent MLN9708, dose-escalation of MLN9708 will continue until the MTD has been identified or a maximum planned dose (MPD) is determined to be safe. Based on experience with other drugs in this condition, it is considered unlikely that patients with systemic AL amyloidosis will tolerate doses higher than those tolerated in other diseases, such as multiple myeloma. Therefore, the maximum dose in patients with systemic AL amyloidosis may be the MTD as recommended from the phase 1 single-agent study of weekly MLN9708 in relapsed/refractory multiple myeloma (C16004). For treatment Cycle 2 and beyond, doses of MLN9708 may be held or reduced in an attempt to manage toxicity according to the guidelines outlined in Section 6.6.

More conservative dose-escalation, evaluation of alternative dosing, and expansion of an existing dose level are all permissible following discussions between the sponsor and the investigators, if such measures are needed for patient safety or for a better understanding of the dose-related toxicity, exposure, or pharmacodynamics of MLN9708.

Treatment repeats every 28 days for 3 cycles. If there is no hematologic response (PR, VGPR, or CR) after completion of 3 cycles of single-agent MLN9708, dexamethasone will be added at the initially recommended dose of 40 mg on Days 1 to 4 of every cycle (d1-4 q28days), beginning in Cycle 4. For patients with fluid retention > 3% of body weight despite optimal diuretic therapy, a starting dose of dexamethasone 20 mg should be considered. The patient's response status will be reassessed after 3 additional cycles; if there

is no hematologic response at that time, the patient will be removed from treatment and followed for survival.

If there is response with MLN9708 alone or dexamethasone and MLN9708, the patient may continue on study for up to 12 cycles of treatment in the absence of PD. Study treatment beyond 12 cycles is allowed only if clinical benefit is clearly indicated after a discussion between the Millennium clinician and the investigator treating the patient.

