The RP2D estimation will be established following evaluation of the available data which will include, but is not limited to, toxicity characterization (Grade 3/4 AEs, SAEs, all grades peripheral neuropathy, and treatment discontinuation) with efficacy (hematologic and organ responses) also taken into consideration. The RP2D will require first cycle DLTs in not more than 0 in 3 or 1 in 6 DLT-evaluable patients enrolled in a single cohort. For the purpose of the RP2D estimation, Cycle 1 data from 6 evaluable patients will be used in addition to the available clinical data supporting tolerance over multiple treatment cycles. AEs that meet DLT criteria in Cycle 2 and beyond will not necessarily influence dose-escalation, but will be considered when determining the RP2D. Toxicities leading to dose modification in Cycle 2 and beyond will not necessarily influence dose-escalation, but will be considered when determining the RP2D.

Once the MTD/RP2D has been established, 2 expansion cohorts of patients with relapsed or refractory amyloidosis, including approximately 10 proteasome inhibitor-naïve patients and approximately 16 proteasome inhibitor-exposed patients, will be treated at the MTD/RP2D to more fully characterize the safety, tolerability, and efficacy of MLN9708, and the PK and pharmacodynamics of MLN9708 in this patient population. As many as 30 patients will be enrolled in the dose-escalation portion of the study, and as many as 20 additional patients (26 in total, including 6 patients from the dose-escalation portion) will be enrolled in the expansion cohorts.

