7.5.13 Pharmacokinetic and Pharmacodynamic Measurements

The timing of the PK and pharmacodynamic blood specimens may be changed if emerging data indicate that an alteration in the sampling scheme is needed to better characterize the PK or pharmacodynamics of MLN9708. The number of specimens may also change, but the number will not increase.

[figure not shown]
Plasma concentrations of the complete hydrolysis product of MLN9708 (ie, MLN2238) will be measured using a GLP-validated liquid chromatography/tandem mass spectrometry assay. Whole blood concentrations of MLN2238 will be measured using a fit-for-purpose liquid chromatography/tandem mass spectrometry assay.

Details regarding the preparation, handling, and shipping of the PK and pharmacodynamic samples are provided in the Study Manual.

The sampling scheme is outlined in the [Pharmacokinetic & Pharmacodynamic Sampling \(Cycle 1\)](#). One blood sample (3 mL) for the determination of plasma concentrations of MLN2238, 1 blood sample (3 mL) for the determination of whole blood concentrations of MLN2238, and 1 blood sample (1 mL) for the measurement of whole blood 20S proteasome activity will be collected at each time point. Blood samples are to be collected during Cycle 1 at the following time points before and after the administration of MLN9708 on Day 1 (MTD cohort patients only) and Day 15 (all patients enrolled in the study): predose (within 1 hour before dosing), and postdose: 30 (\pm 5) minutes, 1 (\pm 0.25) hour, 2 (\pm 0.25) hours, 4 (\pm 0.75) hours, 6 (\pm 0.75) hours, 24 (\pm 1.0) hours (Days 2 and 16), and 168 (\pm 4.0) hours (Days 8 and 22). If feasible, a blood sample for plasma concentration should also be obtained at the time of any drug-related SAE.

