8. STATISTICAL AND QUANTITATIVE ANALYSES

8.1 Statistical Methods

8.1.1 Determination of Sample Size

A 3 + 3 dose-escalation scheme will be conducted, with 3 to 6 DLT-evaluable patients evaluated at each dose level. It is expected that as many as 30 patients will be enrolled in the dose-escalation part of this study.

Once the MTD/R2PD has been established, the following 2 expansion cohorts will be treated at the MTD or RP2D.

1. Proteasome inhibitor-naive expansion cohort including approximately 8 organ response-evaluable patients. There will be approximately 83% probability of observing at least 2 patients with organ responses among 8 patients based on the binomial probability calculation if the overall organ response rate is 35% for this population. Approximately 10 patients will be enrolled to obtain 8 response-evaluable patients.
2. Proteasome inhibitor-exposed expansion cohort including approximately 14 organ response-evaluable patients. There will be approximately 80% probability of observing at least 2 patients with organ responses among 14 patients based on the binomial probability calculation if the overall organ response rate is 20% for this population. Approximately 16 patients will be enrolled to obtain 14 organ response-evaluable patients.

Because approximately 6 patients in the dose-escalation part of the study will be included in the expansion cohorts, approximately 20 patients will be enrolled in the expansion part of this study.

Overall, as many as 50 patients will be enrolled in this study.

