5.4.2 Definition of Baseline Values

Unless otherwise specified, the baseline value is defined as the value collected at the time closest to, but before, the start of study drug administration.

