5.9.2 Pharmacodynamic Analyses

The Pharmacodynamic Analysis population will be used for the description of the pharmacodynamic profile and for the estimation of pharmacodynamic parameters.

The pharmacodynamic measure that will be analyzed is whole blood 20S proteasome inhibition. The inhibition is defined as the postdose proteasome activity times divided by the baseline proteasome activity. If the baseline proteasome activity is missing or is BLQ for a patient, then no inhibition will be calculated for that patient. Individual and mean whole blood 20S proteasome inhibition data will be plotted over time, and summary tabulations will be presented.

Actual specimen collection times will be used for the calculation of pharmacodynamic parameters. In the event that actual collection times are either unreliable or missing, scheduled collection times will be used. For ease of presentation, scheduled collection times will be used to present results in tables and figures. Both scheduled and actual collection times will be presented in listings.

Proteasome activity measurements that are BLQ will be treated as zero. Proteasome activity measurements that are considered anomalous may be excluded from data summaries and plots and will not be used in the calculation of pharmacodynamic parameters. Evidence or explanations will be provided to justify the exclusion of data.

When summarizing proteasome inhibition or pharmacodynamic parameters, a minimum of 2 values is required to show the mean, and at least 3 values are required to show the standard deviation and CV. Summary statistics will be reported only if at least 50% of the values are nonzero.

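### Escalation patients give 20S proteasome samples on Day 15 but none before the first dose, so the SAP calculates no inhibition for them

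*Protocol*

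**What the plan says.** **Sampling.** Footnote a of the Protocol's Cycle 1 sampling table reads: "Day 1, 2 and 8 samples are ONLY collected at the MTD; however, Day 15, 16 and 22 are collected for all patients". Protocol 7.5.13 gives the same split: "Day 1 (MTD cohort patients only) and Day 15 (all patients enrolled in the study): predose (within 1 hour before dosing". The 20S row of the Schedule of Events only points to that table, and no 20S sample is listed at screening.

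**Analysis.** SAP 5.9.2 expresses inhibition relative to baseline activity. SAP 5.4.2 says that, unless specified otherwise, "the baseline value is defined as the value collected at the time closest to, but before, the start of study drug administration", and SAP 5.9.2 gives no separate pharmacodynamic baseline. It then states: "If the baseline proteasome activity is missing or is BLQ for a patient, then no inhibition will be calculated for that patient".

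**What is promised.** Protocol 3.2 lists as a secondary endpoint: "Whole blood 20S proteasome activity profile and inhibition parameters of multiple-dose oral MLN9708". The restriction to the MTD cohort appears only in the neighbouring single-dose PK endpoint. SAP 5.9.2.1 plans summaries of inhibition by dose cohort and day.

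**The concern.** The sampling rule depends on a fact that is normally unknown when the sample is due. Protocol 6.4 identifies the MTD by looking back: a level is named after the next one has produced too many DLTs. Patients at that level, and at all lower levels, have by then taken their first dose.

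These patients still give a full Day 15 series of 20S samples. Without a value before the first dose, the SAP turns none of them into inhibition, so maximum inhibition, its time and the area under the inhibition curve (SAP 5.9.2.2) are also lost. SAP 2.6 requires enough inhibition-time data for membership of the pharmacodynamic population, so these patients leave it. What is at stake is the view of inhibition across doses in a dose-escalation study. Protocol 6.4 names better understanding of dose-related pharmacodynamics as one ground for slowing escalation or expanding a level.

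**Working it through.** The plan states no figure for the number of patients with a 20S baseline. Its head counts agree: 30 + 20 = 50 overall, and 10 + 16 = 26 = 20 + 6 in the expansion set.

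1. **When the MTD is known (Protocol 6.4).** A level clears, the next level opens, two or more DLTs occur there, and the earlier level may then be called the MTD. Patients treated before the higher level opened have passed Day 1. The exception is a second group of three enrolled at the MTD level after the higher level has failed, to reach the 6 evaluable patients used for the RP2D. They could be sampled on Day 1.

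2. **What is collected (sampling table).** Each series has 8 times: predose, 0.5, 1, 2, 4, 6, 24 and 168 hours. Escalation patients give the Day 15 series, which starts after two earlier doses (Days 1 and 8).

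3. **What the SAP does.** Baseline must precede the start of study drug (5.4.2). The Day 15 predose value does not. Baseline is therefore missing, and no inhibition is calculated (5.9.2).

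4. **Count at the ceiling.** With 30 escalation patients, 30 lack a baseline, or 30 − 3 = 27 if the exception in step 1 applies.
   - Share of all patients: 27/50 = 54% to 30/50 = 60%.
   - Samples with no inhibition value: 27 × 8 = 216 to 30 × 8 = 240.

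5. **Count for a short escalation (assumed path).** Take levels of 3, 6 and 3 patients, with the middle level the MTD, followed by 20 expansion patients. Escalation has 3 + 6 + 3 = 12 and the study has 12 + 20 = 32.
   - Without a baseline: 12 − 3 = 9 to 12, so 9/32 = 28% to 12/32 = 38%.
   - Samples: 9 × 8 = 72 to 12 × 8 = 96.

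6. **Within the 26-patient expansion set.** The 6 patients carried over from escalation are affected (6/26 = 23%), or 3 of them (3/26 = 12%) under the exception.

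7. **By dose cohort.** Below the MTD, and at a level above it that failed, the number of patients with an inhibition value is 0. SAP 5.9.1.2 recognises that some doses have only one sampling day, but says so for concentrations only.

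**The case against.** **The count is a maximum.** Thirty escalation patients would need about five full levels or many replacements. Protocol 4.1 and 6.4 also allow the dose recommended from C16004 to serve as the top dose or MTD, which might let that level be recognised in advance. Both points stand and reduce the number. Neither gives the lower levels a baseline.

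**The endpoint is descriptive and only partly lost.** Protocol 1.6 plans limited sampling, no formal test is run, and raw activity on Day 15 is still available for everyone. About 20 expansion patients can describe the effect of the drug in this disease. This stands, and it limits the weight of the point. It does not explain why inhibition by dose cohort is planned when it cannot be calculated.

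**It may be late.** Amendment 4 already refers to accrual data, and the text added by Amendment 6 provides for patients beyond 24 cycles. New sampling may reach few escalation patients. This too stands.

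A reader might infer three stronger things that the documents do not support.

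- *That nobody is sampled on Day 1 if no MTD is reached.* Escalation can end without one ("dose-escalation of MLN9708 will continue until the MTD has been identified or a maximum planned dose (MPD) is determined to be safe"), expansion may run at another dose ("the following 2 expansion cohorts will be treated at the MTD or RP2D"), and later toxicity can move the RP2D ("AEs that meet DLT criteria in Cycle 2 and beyond will not necessarily influence dose-escalation, but will be considered when determining the RP2D"). Read literally, the footnote would then cover no one. However, Protocol 6.4 lets a C16004 dose count as the MTD, the protocol repeatedly pairs MTD with RP2D for the expansion dose, and SAP 5.2 calls the expansion groups MTD cohorts. The sensible reading is the expansion dose.
- *That single-dose PK is lost.* Protocol 3.2 confines it to the MTD cohort by design.
- *That inhibition will be biased by using the Day 15 predose value as baseline.* No document proposes this, and SAP 5.4.2 excludes it. Protocol 1.3.1 reports prolonged inhibition after repeated dosing, but for intravenous twice-weekly treatment, so no size can be given here.

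**Conclusion.** The point holds in a narrow form. Escalation patients normally have no 20S value before the first dose, so under the SAP's own rules their Day 15 samples yield no inhibition, and the planned dose-cohort summaries are empty below the MTD. This conflicts with a secondary endpoint that is not limited to the MTD.

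The size is at most 30 of 50 patients, and plausibly about 9 to 12 of 32 in a short escalation. The first figure rests on the enrolment ceiling and the second on an assumed path. Both assume that the MTD is found by the 3+3 rule and not adopted in advance from C16004, and that expansion patients are sampled on Day 1.

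The damage is confined to a descriptive secondary pharmacodynamic endpoint. DLT counts, the MTD decision and the efficacy analyses do not use these samples. The change is worth making because it is cheap and makes samples already being drawn usable.

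**What to change.** 1. **Baseline sample.** In footnote a and Protocol 7.5.13, require the Day 1 predose 20S sample (1 mL) from every patient at every dose level. Section 7.5.13 rules out more specimens, so either amend that line or drop one Day 15-series 20S point in escalation patients. With the swap, each still gives 8 specimens. The area under the inhibition curve runs from 0 to 168 hours, so an intermediate point is the one to consider.

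2. **Patients already dosed.** Report raw 20S activity only, as SAP 5.9.2 already implies, and say so beside the dose-cohort summaries in SAP 5.9.2.1.

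3. **Wording only.** In the sampling rule, replace MTD by the expansion dose (MTD/RP2D, or MPD). This records the reading most sites would already follow.

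The cost is one 1 mL tube at an existing visit for up to 30 patients, plus short text edits. No patients or visits are added. The downside is that 20S sample handling is needed on Day 1 as well as Day 15 at every dose level, and under the swap one Day 15 point is lost.
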